8.1 Study design

The study is a randomized, double-blind, parallel group, placebo-controlled multicenter study aimed at evaluating the safety and efficacy of rituximab (Mabthera) in the treatment of patients with new-onset MG. The study is expected to be carried out at 10 -15 centers in Sweden. In the study, approximately 50 individuals will be randomized 1: 1 to one of two treatment arms, (1) rituximab or (2) placebo infusion (NaCl).

Possible study participants are informed orally and in writing about the study during in- or outpatient care at the respective neurology clinic and can, after signed consent, be included in the study. *No study-related measures can be carried out before the consent is signed.*

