Starting dose 40 mg / day, with tapering of 5 mg / week until discontinuation.

For patients already on Prednisolone before screening, the pre-screening dose may be increased to 40 mg / day with subsequent tapering according to the above schedule.

To reduce the risk of study endpoints being affected by another MG-specific treatment, such treatment should be given after randomization in accordance with section 10.7, Permitted / non-permitted treatment at different times.

If the cortisone dose can not be reduced due to persistent or worsening clinical symptoms, you may first choose to increase the dose of Prednisolone and make a new plan for phasing out or, secondly, to give rescue treatment with IvIg or PLEX.

Immunosuppressive therapy (azathioprine, ciclosporin, MMF, methotrexate) can be started if indicated from 12 weeks after randomization. Pulse cures with cortisone should not be given after randomization. In cases where the study physician for medical reasons considers that the above treatments are insufficient or inappropriate, other treatment may also be considered, including rituximab. The patient will then be classified as a non-responder in the primary outcome measure and censored in the secondary outcome measures.

Protocoll nr: 2015-00887 Date: 2021-04-26 Version 7.0 (ENG)

7.0 (ENG) 16(42)

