8.5 Evaluation, observation period (24 weeks)

After the single administration of study drug, the effect is followed up according to the following schedule:

- Telephone contact with the study nurse after 2 weeks (+/- 2 days): checking for side effects, verifying current medication and Prednisolone dose.
- Return visit after 4 weeks (+/- 2 days): checking for side effects, verifying current drugs and Prednisolone dose, QMG, MG-ADL, MG-QoL15, EQ5D and somatic status.

Note that QMG testing should be performed 12 hours after the last dose of cholinesterase inhibitors and preferably at the same time of day throughout all testing sessions.

- Telephone contact with a nurse after 8 weeks (+/- 4 days): checking for side effects, verifying current medication and Prednisolone dose.
- Telephone contact with a nurse after 12 weeks (+/- 4 days): checking for side effects, verifying current drugs and Prednisolone dose.
- Return visit after 16 weeks (+/- 21 days): checking for side effects, verifying current drugs and Prednisolone dose, QMG, MG-ADL, MG-QoL15, EQ5D and somatic status.

Note that QMG testing should be performed 12 hours after the last dose of cholinesterase inhibitors.

Important: a serum tube for exploratory immunological analyzes is taken and sent to the sample management Karolinska University Hospital Solna, attach study-specific consultant referral.

- Telephone contact with a nurse after 20 weeks (+/- 7 days): checking for side effects, verifying current drugs and Prednisolone dose.
- Return visit after 24 weeks (+/- 21 days): checking for side effects, verifying current drugs and Prednisolone dose, QMG, MG-ADL, MG-QoL15, EQ5D and somatic status.

Note that QMG testing should be performed 12 hours after the last ingestion of cholinesterase inhibitors.

Important: a serum tube for exploratory immunological analyzes is taken and sent to the sample management Karolinska University Hospital Solna, attach study-specific consultant referral.

At the centers that have a neurophysiology clinic at the hospital, a repetitive nerve stimulation will be performed in connection with the return visit or in close proximity to the visit, see section 11.6 Neurophysiology.

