13.1 Deciding on number of study subjects

Based on results reported in Sanders DB et al.², our own experience, and a shorter phasing out of cortisone than used in most protocols, it is estimated that \leq 40% in the placebo group achieve the primary endpoint of a daily Prednisolone dose \leq 10mg with QMG \leq 4. With 25 patients in each arm, the power will be 0.85 with an alpha = 0.05 for a two-sided test of 80% reaching the primary endpoint of the active arm.

[Note, due to slow recruitment the funder of the study, the Swedish MRC, requested a revised power calculation. March 15th 2018 the following text was submitted, which was approved May 25th 2018:

"The study regards a study drug being administered on only one occasion, with determination of main endpoints at 4 and 6 months, respectively. Possible drop-outs are therefore limited to study participants actively interrupting the study, including the follow-up visits that the protocol stipulates, or that dies before these visits. Of a total of 23 included study participants, none have interrupted. One study participant died due to a medical condition not considered directly related to the study medication. A revised power calculation with the same input variables (without loss) shows that with the same number of patents in each treatment arm: 20 per arm (N = 40), power = 81%; 22.5 per arm (N = 45), power = 85%; 25 per arm (N = 50), power = 89%. Based on interim results, it is therefore reasonable to expect a dropout rate <5%. In order to maintain a power of at least 80% and a certain margin for any minor imbalance in the randomization, n≥45 is needed." The power calculation provided in the paper is based on this revised calculation.]

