13.2 Analysis plan

Differences in the primary endpoint will be tested on an intention-to-treat basis using Fisher's exact test. As a secondary analysis, the primary endpoint will also be analyzed with log-binomial regression, adjusted for any observed baseline differences that have occurred despite randomization.

Patients who have received disease-modulating MG treatment as indicated in section 10.7 as "Not allowed" after randomization and before the assessment visit at 16 weeks will be counted as non-responders.

In addition to the primary efficacy variable, a few secondary outcome measures of particular clinical relevance have been selected to reduce the risk of false-positive findings. Differences in the change of these continuous measures will be tested with the Mann-Whitney U-test. P-values will be adjusted with Bonferroni correction for these three tests. To estimate 95% confidence intervals around the difference, linear regression with robust standard errors will be used, without adjustment for the number of tests. Patients who have received disease-modulating MG therapy as indicated in section 10.7 as "Not allowed" after randomization and before the assessment visits at 16 and 24 weeks will be censored from the time these treatments were administered.

A challenge in clinical trials is the management of dropouts, which risks introducing a selection error if response data are only available to the patients who remain in the study. As this study only involves study drug administration at baseline, we expect that the drop-out rate, and thus the need for imputation for those who have left the study, will be limited. If the dropout rate is higher than 10%, imputation will be performed, partly with multiple imputation with explicit modeling of the treatment outcome as a function of baseline variables (age, gender, disease activity), partly through so-called "last observation carried forward", where values for patients who left the study are replaced with their most recently observed value. However, it is very important to emphasize the

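### The multiple-imputation model in section 13.2 leaves out the randomised arm, so imputed data would pull the treatment difference towards zero by about the missing fraction

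*Combined protocol and SAP*

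**What the plan says.** Section 13.2 (Analysis plan) imputes only when dropout is above 10%. It names two methods and does not say which is the main one. The first is "multiple imputation with explicit modeling of the treatment outcome as a function of baseline variables (age, gender, disease activity", a list made up entirely of pre-randomisation variables. The second is LOCF, "where values for patients who left the study are replaced with their most recently observed value". Neither there nor elsewhere does the plan add the randomised arm to the model, mention imputing within arm, or use post-baseline scores.

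The data that could be used are set out in section 8.5 and Annex 1. Between V.0 and week 16 the only scored visit is week 4: "Return visit after 4 weeks (+/- 2 days): checking for side effects, verifying current drugs and Prednisolone dose, QMG" (MG-ADL and MG-QoL15 are scored then too). Prednisolone dose is also checked by telephone at weeks 8 and 12.

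Section 8.4 gives the prednisolone schedule: "Starting dose 40 mg / day, with tapering of 5 mg / week until discontinuation". It applies only where the treating physician judges steroids indicated, and may begin after screening or on the day after infusion. The primary endpoint (section 7.1) requires QMG of 4 or less, prednisolone of 10 mg/day or less and no rescue treatment at week 16.

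**The concern.** An imputation model should contain every variable in the analysis model, and the arm above all. If it does not, a missing rituximab outcome and a missing placebo outcome with the same baseline values are drawn from the same distribution, as if treatment had no effect in dropouts. The estimated effect is then diluted by the imputed share. Section 13.2 gives selection error among dropouts as its reason to impute, but baseline variables alone cannot correct dropout that depends on early response.

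LOCF raises a separate, smaller question. The week-4 QMG may be measured in the middle of the steroid taper, and the composite has a dose component that is recorded more often than the QMG. What is carried forward, and from which date, is not defined.

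**Working it through.** **Planning figures.** Section 13.1 assumes at most 40% response on placebo and states: "With 25 patients in each arm, the power will be 0.85 with an alpha = 0.05 for a two-sided test of 80" per cent on rituximab. The pooled-variance normal approximation at 25 per arm gives z = (0.40 − 1.96 × √(2 × 0.6 × 0.4/25)) / √((0.24 + 0.16)/25) = (0.40 − 0.272)/0.126 = 1.015, so power is 0.845, matching the stated 0.85. The revised figures ("20 per arm (N = 40), power = 81%; 22.5 per arm (N = 45), power = 85%; 25 per arm (N = 50), power = 89" per cent) are reproduced by the unpooled form, z = 0.40/√(0.40/n) − 1.96, which gives 0.807, 0.851 and 0.885. Both sets rest on 40% against 80%, so these rates are used below.

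**Trigger.** 4/47 = 8.5% and 5/47 = 10.6%, so five dropouts are enough.

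**Imputation without arm, primary endpoint.** Let d be the missing fraction, assumed random and equal in both arms, with 1:1 allocation. Baseline variables are balanced by randomisation in expectation and cannot stand in for arm. The imputed response rate in each arm is therefore (40 + 80)/2 = 60%.

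- Placebo: 40(1 − d) + 60d
- Rituximab: 80(1 − d) + 60d
- Difference: 40(1 − d)

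| Missing | Difference (points) |
|---|---|
| 0% | 40 |
| 11% | 35.6 |
| 15% | 34 |
| 20% | 32 |

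**Continuous outcome.** This was simulated with 47 patients, 3,000 runs, a true effect of 1 SD and random dropout. The assumed correlation of the week-16 score with baseline was 0.5, and with week 4 it was 0.70 within arm. The documents give none of these values.

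| Missing | No arm | Arm | Arm + week 4 |
|---|---|---|---|
| 10% | 0.90 | 1.01 | 1.01 |
| 15% | 0.84 | 0.99 | 0.99 |
| 20% | 0.81 | 1.01 | 1.01 |

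Omitting arm causes the shrinkage. Under random dropout, adding week-4 scores to arm does not move the mean estimate. Their role is precision, and protection when dropout depends on early response.

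**Power.** No power loss is claimed. Treating imputed values as observed, Fisher's test with 23 and 24 patients falls from 0.799 to 0.646 at 15% missing. But simply analysing 20 and 20 patients (7 of 47 lost, 14.9%) gives 0.650. On that crude comparison the fall reflects lost information, not the missing arm term.

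**LOCF and the taper.** For a taper begun on the day after infusion (day 1), the schedule gives:

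- days 22–28: 25 mg; days 29–35: 20 mg
- days 50–56: 5 mg; from day 57: 0 mg

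The week-4 visit (days 26–30) falls at 20 to 25 mg/day. The week-8 call (days 52–60) falls at 5 or 0 mg/day. For a patient on this schedule lost after the week-8 call and before week 16:

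- carrying the whole week-4 visit forward gives a dose above 10 mg/day, hence a non-responder whatever the QMG;
- carrying each component separately pairs a week-4 QMG with a dose of 5 or 0 mg/day, so the patient may be a responder.

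For continuous scores, if a share f of the week-16 effect is already present at week 4, LOCF for patients lost between weeks 4 and 16 gives (1 − d) + d × f. At d = 10% this is 0.90, 0.95 and 1.00 for f = 0, 0.5 and 1 (simulated: 0.90, 0.95, 1.01). The documents do not give f.

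**The case against.** The strongest reply is that this is a fallback unlikely to be used. Section 13.1 expects dropout below 5% and reports no interruptions and one death among the first 23 participants. Just above the trigger the loss is about 4 points, and the 20% row is remote. Shrinkage towards zero does not raise the false-positive risk. The variable list may also be shorthand, with arm intended. All of this bears on likelihood and severity, and it stands. It does not remove the defect: nothing in the text adds arm, and a fallback must work in the case it is written for.

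A reader might infer three stronger things that the documents do not support.

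- *That LOCF makes every dropout on the taper a non-responder on dose alone.* Prednisolone is conditional and may start after screening. A start 14 days earlier puts week 4 on taper days 40–44, at 15 or 10 mg. Doses are also recorded at weeks 8 and 12. Patients lost before week 4 carry baseline, and those lost after week 16 carry week 16 to week 24.
- *That LOCF is biased in a known direction.* It depends on how much of the effect is present at week 4 and on who drops out, and neither is given.
- *That omitting week-4 scores biases the result in itself.* Under random dropout it does not.

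**Conclusion.** The point holds for the imputation model. As written it omits the randomised arm, and the expected difference is multiplied by about one minus the missing fraction: a loss of 4.4, 6 and 8 points out of 40 at 11%, 15% and 20% missing. This rests on the planning rates, on random dropout equal in the two arms, and on the listed variables being the whole model. With unequal or informative dropout the size would differ.

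Omitting week-4 scores (and week-16 scores for the week-24 QMG) is a lesser fault: lost precision, plus bias if dropout depends on early response. Its size was not estimated.

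For LOCF, what can be said is that the rule for the composite is undefined and can classify the same patient either way. The point is worth correcting but not critical, because it operates only with five or more dropouts of 47.

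**What to change.** In section 13.2:

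- State that the imputation model includes randomised arm, or that imputation is done within arm. This alone removes the demonstrated bias.
- Add V.0 score, prednisolone dose at V.0 and all observed post-baseline scores (week 4, and week 16 for the week-24 QMG), with age and sex. If 47 patients cannot support every term, arm should be the last to be dropped.
- Say whether the composite is imputed directly or through its components.
- Name this as the main method for missing data.
- Keep LOCF, if at all, as a sensitivity analysis with a stated rule: whole visit or component by component, and from which contact.

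A tipping-point analysis that varies the imputed values by arm is an optional addition.

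The cost is wording only. Every variable is already collected under section 8.5 and Annex 1. If arm was always intended, one sentence settles the main point.

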13.3 Data handling and Case Report Forms, CRF

importance of including complete study data on as many subjects as possible.

Other measures are tertiary or exploratory.

Data collected in the study are registered by the study staff in paper CRF (source document), where certain information is also entered in specially modified pages in the Swedish MG register (MGreg). This concerns rating scales, dates of follow-up visits, cortisone dose, possible side effects and any need for other MG-specific therapy (rescue treatments). This part of MGreg belongs to the decision support and not the quality register part of MGreg. MGreg is located on the same platform as the other sub-registries in the Swedish Neuroregister and is accessed in the usual way by logging in from a computer with an Internet connection. For patients who give consent to registration in the MGreg quality registry part, results from the assessment scales are also transferred to this part. However, the study does not require the consent of the quality registry section.

Patient data is collected according to the protocol and registered continuously in paper CRF (source documents), with duplication of certain information in MGreg CRF. For each contact occasion, there is a page with the necessary

Protocoll nr: 2015-00887 Date: 2021-04-26

Version 7.0 (ENG) 27(42)

information to fill in. When extracting data from MGreg (the decision support part), the patient's name and social security number are deleted, so that only the patient number in MGreg remains. This number is thus the link to the person's name and social security number and is available only to the investigators and nurses who work locally at the patient's clinic and people who work with quality assurance of the study. All withdrawals from the registry are logged.

Information entered in MGreg is locally available to each investigator even after the end of the study.

All blood samples leaving the hospital will also be marked with this patient number only. No unauthorized person will have access to the code key.

Collected data originates in source documents at the clinic such as lab reports and other test results and results.

13.4 Data processing

Data processing and statistical analysis will be carried out by the coordinating investigator in collaboration with biostatisticians at the Department of Medicine, Karolinska University Hospital Solna. A compilation of study data is distributed to participating investigators when the study is completed.

Data processing can begin after the last patient has completed the last visit in the study.

13.5 Archiving

Data collected during the study will be archived for at least 10 years after the study is completed.

14 Quality control

14.1 Source data

Source data in the study are the patient's medical record, paper CRF for all contact sessions, questionnaires / assessment scales as well as transcripts such as analysis answers and lab lists.

At each center, a source data document will be drawn up specifying what is the source data for the center.

14.2 Monitoring

To ensure that the study is conducted according to the protocol, that data is collected, documented, and reported in accordance with ICH-GCP (Good Clinical Practice) and current ethical and regulatory requirements, the study will be monitored by an external party before the study begins, during the study and after that the study has been completed.

The monitoring also aims to ensure that the subject's rights, safety, and well-being are met and that the data in the CRF are filled in, correct and in accordance with the source data.

14.3 Access to source data

Study monitors can gain access to medical records and source data after a confidentiality agreement has been signed by the medical record manager at the clinic and monitor. The accuracy of data entered in MGreg will be checked against source documents.

15 Ethics

15.1 Ethical review board and Medical Products Agency

The sponsor / coordinating investigator is responsible for ensuring that the application for approval for the implementation of the study is obtained from the Regional Ethics Review Board and the Medical Products Agency.

Additions to or significant changes to the protocol can be made after the application for an addition / amendment has been approved by the Regional Ethics Review Board and / or the Medical Products Agency.

15.2 Ethical conditions for the study

The study will be conducted in accordance with the protocol and the latest version of the Declaration of Helsinki, ICH-GCP and other applicable ethical and regulatory laws, rules, and requirements.

Patients are informed orally and in writing about the study and are informed that participation in the study is completely voluntary and that participation can be interrupted at any time, regardless of the reason, without this affecting the patient's future treatment in any way.

The patient is informed that the data collected until the interruption will be analyzed.

Protocoll nr: 2015-00887 Date: 2021-04-26

Version 7.0 (ENG) 28(42)

Data collected during the study are coded so that no individual can be distinguished.

15.3 Benefit risk assessement

During the study, blood samples will be taken and an intravenous catheter inserted for the administration of study drugs. For most patients, the placement of intravenous catheters and needle punctures for blood sampling is well tolerated. In rare situations, however, they can cause bleeding, bruising, swelling, coagulation in the vein, leakage of medication or solution into the surrounding tissues, and possibly infection at the site of insertion of the needle or catheter. Sampling and insertion of an intravenous catheter will be performed according to clinical practice by staff with extensive experience in this field.

As with all medicines, rituximab can cause side effects, although well tolerated compared to other biological medicines. The side effects of rituximab are usually mild or moderate. The investigator will discuss possible side effects with the patient and explain the risks and benefits of rituximab before treatment. Because rituximab is being studied in MG patients, not all possible side effects are known.

Very common side effects (affects at least 1 in 10 patients) include fever, itching, redness of the skin, nausea, headache.

Common side effects (affects 1 or more in 100 patients and less than 10 in 100 patients) include: reduced platelet count, abdominal pain, constipation, vomiting, diarrhea, stomach discomfort after meals, nausea, chest discomfort, chills, infusion-related reaction, anaphylactic reaction, edema, fever, tiredness, weakness, cold sores, cold, viral infection, stomach flu, bronchitis, severe infection, muscle aches, back and neck pain, pain in limbs and joints, muscle cramps, dizziness, disturbances in taste, tingling of the body, vertigo, high blood pressure, difficulty or pain when urinating, spontaneous erection, upper respiratory tract infection, pneumonia, urinary tract infection, joint infection, cough, irritation or pain in the throat, nasal congestion, itchy skin, rash, hair loss, and dry skin.

In addition, serious infections, sepsis, and infusion reactions have been reported in patients receiving rituximab and these are identified safety hazards.

Patients receiving rituximab will have a weakened immune system, which may affect the patient's ability to fight viral and bacterial infections. Patients treated with rituximab have an increased risk of worsening certain chronic infections, such as hepatitis B.

Based on what has been described above, the risks that study participation entails are considered acceptable given that the study population includes patients with new-onset moderate to severe MG (moderate to severe effects on ADL), which is a condition that risks deteriorating further if immunomodulatory treatment is not instituted, in turn involving other types of risks such as osteoporosis, poor blood sugar control and other side effects of cortisone.

The patient's condition may improve, remain the same, or worsen during the study. If the study and possibly other studies with rituximab in MG are positive, this may lead to benefit for other patients, as clinical evidence for efficacy with this drug is then substantiated. It is worth mentioning that today there is a complete lack of approved treatments for MG and that clinical practice is based entirely on proven experience. We believe that this will affect national practice for the treatment of MG.

